8.5 INTERIM ANALYSIS

There is no formal interim analysis planned for this study.

8.6 SAMPLE SIZE

The study is planned to enrol up to 12 participants with geographic atrophy secondary to age-related macular degeneration with visual acuity (20/32 to 20/2000, Snellen's equivalent), following the 3+3 method.

The sample size chosen for this study was selected without formal statistical justification, but the numbers chosen are considered adequate for assessing the study objectives. The sample size was determined on the basis of practical and logistical considerations and not based on statistical power with regard to hypothesis testing or precision with regard to parameter estimation.

This phase 1 trial was designed to identify any important limiting toxicities and to determine if this dose is suitable for phase 2 trial. This was also designed to minimize the likelihood that a minimum number of subjects will be exposed to the investigational drug.

This is an open label study, and no randomization is conducted in this study.

8.7 MISSING DATA

Missing data will generally not be imputed for safety or efficacy data.

9 DATA COLLECTION, RETNETION AND MONITORING

9.1 DATA COLLECTION INSTRUMENTS

The investigator will prepare and maintain adequate and accurate source documents designed to record all observations and other pertinent data for each participant treated with the study drug.

Study personnel at each site will enter data from source documents corresponding to a participant's visit into the protocol-specific electronic Case Report Form (eCRF) when the information corresponding to that visit is available. Participants will not be identified by name in the study database or on any study documents to be collected by the Sponsor (or designee), but will be identified by a site number, participant number and initials.

If a correction is required for an eCRF, the time and date stamps track the person entering or updating eCRF data and creates an electronic audit trail. The Investigator is responsible for all information collected on participants enrolled in this study. All data collected during the course of this study must be reviewed and verified for completeness and accuracy by the Investigator. A copy of the CRF will remain at the Investigator's site at the completion of the study.

9.2 DATA MANAGEMENT PROCEDURES

The data will be entered into a validated database. The Data Management group will be responsible for data processing, in accordance with procedural documentation. Database lock will occur once quality assurance procedures have been completed. All procedures for the handling and analysis of data will be conducted using good computing practices meeting FDA guidelines for the handling and analysis of data for clinical trials.

9.3 DATA QUALITY CONTROL AND REPORTING

After data have been entered into the study database, a system of computerised data validation checks will be implemented and applied to the database on a regular basis. Queries are entered, tracked, and resolved through the EDC system directly. The study database will be updated in accordance with the resolved queries. All changes to the study database will be documented.

9.4 ARCHIVAL DATA

The database is safeguarded against unauthorised access by established security procedures; appropriate backup copies of the database and related software files will be maintained. Databases are backed up by the database administrator in conjunction with any updates or changes to the database.

At critical junctures of the protocol (e.g., production of interim reports and final reports), data for analysis is locked and cleaned per established procedures.

9.5 AVAILABILITY AND RETENTION OF INVESTIGATIONAL RECORDS

The Investigator must make study data accessible to the monitor, other authorized representatives of the Sponsor (or designee), IRB/IEC, and Regulatory Agency (e.g., FDA, TGA) inspectors upon request. A file for each participant must be maintained that includes the signed informed Consent, HIPAA Authorization and Assent Form and copies of all source documentation related to that participant. The Investigator must ensure the reliability and availability of source documents from which the information on the eCRF was derived.

All study documents (patient files, signed informed consent forms, copies of eCRFs, Study File Notebook, etc.) must be kept secured for a period of fifteen years following the completion of the study.

9.6 MONITORING

Monitoring visits will be conducted by representatives of the Sponsor according to the U.S. CFR Title 21 Parts 50, 56, and 312 and ICH Guidelines for GCP (E6). By signing this protocol, the investigator grants permission to the Sponsor (or designee), and appropriate regulatory authorities to conduct on-site monitoring and/or auditing of all appropriate study documentation.

9.7 DATA SAFETY MONITORING BOARD

An independent DSMB will be convened. The mission of the DSMB will be to ensure the ethical conduct of the trial and to protect the safety interests of patients in this study. The DSMB will be responsible for reviewing the cumulative safety results from the study. The DSMB will meet prior to the commencement of the study, and will review all

available safety/tolerability data (e.g., adverse events, serious adverse events, clinical laboratory assessments, blood pressure, haematology, urology) at Day 0 and 1 month after IVT injection of FCA of the initial participant in Part 1 and 3 (prior to Part 2 & 4 of the study), and convene as required throughout the study period to review data and potential safety risks. The criteria for evaluating study continuation will relate to study safety, including the incidence and severity of ocular and/or systemic side effects not limited to but including; change in IOP of >10mmHg, a loss of 15 letters or more in BCVA, presence or intraocular inflammation, presence or absence of ocular pain, change in BP of 30mmHg (systolic or diastolic), incidence of hospitalisation or systemic illness, and any other ocular or systemic adverse events reported. Any changes will be referenced to baseline measurements. The DSMB will then meet at the conclusion of the study and after the final statistical analysis in order to review all data.

DSMB will consist an ophthalmologist, and a biostatistician, both independent of the study team.

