1.1 SYNOPSIS

Title:	A Phase 1b, study of safety and tolerability of Intravitreal Fludrocortisone acetate (FCA in Patients with Geographic Atrophy (GA)
Sponsor:	Eye Co Pty Ltd
Protocol Number, Version and Date:	EC-FCA-001/ Version 1.3 / 22 January 2020
Investigational Product, Dose and Route of Administration:	Fludrocortisone acetate (FCA) 1mg/0.1ml & 2mg/0.1ml Intravitreal (IVT) injection
Rationale for dose:	
Single dose of 0.1 ml in a concentration of 1mg/0.1 mL and 2mg/0.1mL was selected based on previous pre-clinical model (Kivilcim et al). There were no signs of retinal toxicity on slit-lamp examination, indirect ophthalmoscopy, or by light microscopy in all eyes injected with 400µg/0.1mL, 1mg/0.1mL and 2mg/0.1mL. However, it was reported 1 case of intravitreal haemorrhage in 4 mg/0.1 mL.
 
Systemic injection of Fludrocortisone acetate has serious mineral corticoid and glucocorticoid side effects such as hypertension, potassium loss, Cushingoid changes, etc. Intravitreal injection fludrocortisone acetate may avoid systemic side effects.

Objectives:	To determine safety and tolerability of a single dose intravitreal (IVT) injection of 1mg/0.1mL and 2mg/0.1mL FCA in subjects

with GA secondary to Age-Related Macular Degeneration (AMD).

Study Population: Study population will comprise of patients with GA secondary to AMD in both eyes with no previous treatment. The study is planned to enrol up to 9 participants.

Study Design: This study is planned to enrol 9 participants to assess dose escalation based on a 3+3 algorithm. Enrolment will stop if > 2 patients experience dose-limiting toxicity at any time during the study. Dose-limiting toxicity is defined by intraocular inflammation, elevated IOP, reduced vision (loss of ≥ 15 letters), or haemorrhage within 28 days after injection.

Part 1 involves a single participant to assess safety and tolerability of 1mg/0.1mL FCA. This participant will be followed for up to 28 days and reviewed by a safety review committee prior to the recruitment of a further 2 participants treated with 1mg/0.1mL FCA totalling in 3 participants in the first cohort.

Part 2 involves a single participant to assess safety and tolerability of 2mg/0.1mL FCA. This participant will be followed for up to 28 days and reviewed by an independent safety review committee prior to the recruitment of a further 5 participants treated with 2mg/0.1mL FCA totalling in 6 participants in the second cohort.

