5.2 TREATMENTS ADMINISTERED

5.2.1 DOSE LEVELS AND STUDY ARMS

A single dose of 1- and 2 mg Fludrocortisone acetate/0.1mL will be tested in this study. Subjects will receive 1 IVT injection as outlined in the table below.

	Treatment Arm	Dose Escalation
Part 1	Fludrocortisone acetate 1 mg/0.1mL at Day 0	If no dose limiting toxicity is observed in 3 patients at this given dose level, the dose will be escalated to the following level:
Part 2	Fludrocortisone acetate 2 mg/0.1mL at Day 0	

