6.2 SUBJECT ENROLLMENT

It is the responsibility of the investigator to ensure that subjects are eligible to participate in the study prior to enrollment and throughout the study. Documentation of the personally signed and dated informed consent of each subject, using the study-specific ICF, is required before initiating the Screening process. After written informed consent has been obtained and eligibility to participate established, investigative site personnel will obtain the subject's identification number. Only eligible subjects will be allocated to the open label FCA 1 mg/0.1mL or 2mg/0.1 mL.

Enrollment will occur in two parts in order to minimise the likelihood that subjects will be exposed to risks. During part 1 & 2, subjects will be screened one by one as only one patient will initially be enrolled during part 1 of the trial. The first enrolled subject will participate in a screening period of up to 14 days and a follow-up period of 28 days, to detect an IOP response.

After first subject has completed the follow-up of 28 days after FCA 1mg/0.1 mL injection, The subject's safety data will be reviewed the safety data of this will be reviewed by an independent safety review committee to determine whether to commence enrolment of additional 2 patients in the first cohort of 1mg/0.1mL dose of FCA. Enrolment will be stopped if >2 patients experience limiting-toxicity adverse event related to the study drug. If no more than two adverse events considered to be related to the study drug occur with limiting toxicity, the second cohort will be recruited. Dose-limiting toxicity is defined by intraocular inflammation, elevated IOP, reduced vision (loss of ≥ 15 letters), or haemorrhage within 28 days after injection.

Part 2 will take in place if the 3 subjects have tolerated well the dose. Part 2 initially involves a single subject treated with 2mg/0.1mL FCA to assess safety and tolerability. This subject will be followed for up to 28 days and reviewed by an independent safety

review committee prior to the recruitment of a further 5 subjects treated with 2mg/0.1mL FCA totalling in 6 subjects in the second cohort.

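### No section requires a review of the full 1 mg cohort before the first 2 mg injection, Section 9.7 counts four parts in a two-part study, and the escalation rule is stated in conflicting ways

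*Protocol*

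**What the plan says.** **Parts.** The synopsis, Section 2.3.3, Section 5.2.1 and Section 6.2 all describe two parts. Part 1 is 1 mg (one participant, then two more) and Part 2 is 2 mg (one participant, then five more). Section 9.7 instead sets DSMB reviews "at Day 0 and 1 month after IVT injection of FCA of the initial participant in Part 1 and 3", with the qualifier "prior to Part 2 & 4 of the study". The DSMB may also meet as needed during the study.

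**Reviews.** In the synopsis the first 1 mg participant has up to 28 days of follow-up and is then "reviewed by a safety review committee prior to the recruitment of a further 2 participants treated with 1mg/0.1mL FCA". The first 2 mg participant is handled in the same way before a further five are recruited. Section 6.2 repeats both steps and gives the first enrolled subject "a follow-up period of 28 days, to detect an IOP response".

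**DLT window.** The synopsis and Section 6.2 define DLT as intraocular inflammation, raised IOP, loss of 15 or more letters, "or haemorrhage within 28 days after injection".

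**Escalation.** There are three statements:
- Section 5.2.1 escalates on this condition: "If no dose limiting toxicity is observed in 3 patients at this given dose level".
- Section 6.2 says that if "no more than two adverse events considered to be related to the study drug occur with limiting toxicity, the second cohort will be recruited".
- The next paragraph of Section 6.2 says "Part 2 will take in place if the 3 subjects have tolerated well the dose".

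**The concern.** Section 2.3.3 says that the drug has not been given intravitreally to humans and offers the staged design as the mitigation. Doubling the dose is the main safety decision in that design. The protocol should therefore fix three things: when the decision is taken, on whose completed follow-up, and by what rule. It spells out 28 days and a committee review for the first participant at each dose, but not for the step from 1 mg to 2 mg. It then gives rules for that step that disagree. A site and a safety committee could each follow the text and reach different decisions.

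**Working it through.** There is no planned figure to reproduce, so the check is mainly a comparison of sections.

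**1. Parts.** Parts defined: 2. Parts named in 9.7: 1, 2, 3 and 4. Parts 3 and 4 appear nowhere else.

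**2. What each reading of 9.7 provides before the first 2 mg injection.**
- *Literal, two parts.* The one-month review follows the initial 1 mg participant. Under 6.2 that review decides whether to enrol participants 2 and 3, so they have not yet been dosed. Part 3 has no meaning.
- *Four steps (first participant, then expansion, at each dose).* The one-month reviews again follow only the first participant at each dose. A Day 0 review falls on the day of the first 2 mg injection, but it is not said to come before the injection or to need any minimum follow-up in participants 2 and 3.

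Fixed 28-day or one-month reviews during enrolment are thus tied to 1 of 3 participants at 1 mg and 1 of 6 at 2 mg. Required reviews of 1 mg participants 2 and 3 after Day 28 and before 2 mg: 0 on either reading.

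**3. The escalation rule by outcome in the 1 mg cohort**, counting one related, clinically significant DLT per affected participant:

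| Affected, of 3 | Section 5.2.1 | 6.2, count sentence | 6.2, tolerance paragraph |
|---|---|---|---|
| 0 | met | met | met, if no other significant drug-related event or laboratory abnormality |
| 1 | not met | met | not met |
| 2 | not met | met | not met |
| 3 | not met | not met | not met |

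The count sentence disagrees with the other two at 1 and at 2.

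**4. How often that could arise (illustration).** The protocol gives no DLT rate. Assume a 28-day risk p per participant, with independent participants. The chance of 1 or 2 affected among 3 is 1 − (1−p)³ − p³:
- p = 0.1: 1 − 0.729 − 0.001 = 0.270
- p = 0.2: 1 − 0.512 − 0.008 = 0.480
- p = 0.3: 1 − 0.343 − 0.027 = 0.630

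The chance of at least one DLT in participants 2 and 3, whom no fixed 28-day review covers, is 1 − (1−p)² = 0.19, 0.36 and 0.51. This is not the chance that such an event is missed, because adverse events are reported throughout.

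**5. Delay from adding the review.** The wait is 28 days. Time to convene is not given; 7 days is assumed, which makes 28 + 7 = 35 days. For time to the last of 9 injections, assume s days of screening each, no overlap, and 7 days to convene every review:
- Now: 9s + 2×28 + 2×7 = 133 days (s = 7) or 196 days (s = 14, the maximum).
- With the added review: 9s + 3×28 + 3×7 = 168 or 231 days.
- To stay within 6 months (about 183 days): s ≤ (183 − 105)/9 = 8.7 days.
- At s = 14, with screening run during all three waits, six screenings add time: 6×14 + 84 + 21 = 189 days.

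**The case against.** The case for the protocol has three parts, and much of it stands.

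*The wait is implied.* A condition of no DLT in three patients, with DLT defined over 28 days, cannot be met while any window is open. This is right. A reader might infer that 2 mg dosing could properly start with much of participant 3's window unobserved. The documents do not support that, because it means setting the DLT definition aside and assuming dosing intervals that the protocol does not give. The wait still has to be deduced, whereas the same text states it for each first participant, and deduction supplies no committee review.

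*The numbering is an editorial slip.* A reader might infer from 9.7 that the first 2 mg participant would go unreviewed. That does not follow: the synopsis and 6.2 independently require 28 days and a committee review before the other five are recruited. The four-step meaning is also easy to see. What remains is the gap between the 1 mg expansion and the first 2 mg dose, and the DSMB's discretion to meet when needed does not fill it with a requirement.

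*Section 6.2 read whole is stricter than its one sentence.* A reader might infer that 6.2 lets escalation proceed almost whatever happens at 1 mg. It does not: its next paragraph requires that the three subjects tolerated the dose, and tolerance is defined as no clinically significant drug-related event or laboratory abnormality. The synopsis applies the limit of more than two patients at any time in the study, which suggests that it was meant as a study-wide stopping limit. The sentence also counts events rather than patients. All of this stands, but the sentence still says in terms that the second cohort will be recruited, so the contradiction remains.

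**Conclusion.** The point holds and should be fixed, though it is a gap and a contradiction in the text rather than a missing safety system. Section 9.7 names two parts that do not exist. No section requires a review of two of the three 1 mg participants after Day 28 and before the dose is doubled. With 1 or 2 DLTs at 1 mg, one sentence of 6.2 supports escalation while 5.2.1 and the next paragraph of 6.2 do not.

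The count of required reviews and the contradiction rest on the text alone. The figures 0.27, 0.48 and 0.63 rest on assumed risks, independence and one related event per affected participant. They measure how often 5.2.1 and that one sentence would part, not how often 6.2 taken as a whole would lead to escalation.

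**What to change.** 1. Renumber Section 9.7 to the two-part design. If a Day 0 review is kept, say that it precedes the injection.
2. State that the first 2 mg injection may be given only when all three 1 mg participants have completed Day 28, their cumulative safety data have been reviewed, and the 5.2.1 condition is met.
3. Delete the sentence in 6.2 that allows up to two related limiting toxicities, or align it with 5.2.1. Keep the limit of more than two patients only as a study-wide stopping limit.
4. State which body, the DSMB or the safety review committee, makes each review. The protocol does not say whether they are the same.

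The cost is protocol wording and one extra meeting, using Day 28 visits already in the Schedule of Activities. The delay is up to about 4 weeks plus time to convene, about 35 days on the 7-day assumption. A site that already infers the wait loses only the convening time. The 6-month recruitment period may be strained if screening runs near 14 days. On the assumptions above it is exceeded there even when screening overlaps the waits (189 days against about 183), and without overlap it would be exceeded already without the added review (196 days). The sponsor should allow for this in the stated duration.

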9.8 PARTICIPANT CONFIDENTIALITY

In order to maintain participant confidentiality, only a site number, participant number and participant initials will identify all study participants on eCRFs and other documentation submitted to the Sponsor. Additional participant confidentiality issues (if applicable) are covered in the Clinical Study Agreement.

10 ADMINISTRATIVE, ETHICAL, REGULATORY CONSIDERATIONS

The study will be conducted according to the Declaration of Helsinki, Protection of Human Volunteers (21 CFR 50), Institutional Review Boards (21 CFR 56), and Obligations of Clinical Investigators (21 CFR 312).

To maintain confidentiality, all laboratory specimens, evaluation forms, reports and other records will be identified by a coded number and initials only. All study records will be kept in a locked file cabinet and code sheets linking a patient's name to a patient identification number will be stored separately in another locked file cabinet. Clinical information will not be released without written permission of the participant, except as necessary for monitoring by the TGA. The Investigator must also comply with all applicable privacy regulations (e.g., *The Health Records and Information Privacy Act 2002*).

10.1 PROTOCOL AMENDMENTS

Any amendment to the protocol will be written by the Sponsor. Protocol amendments cannot be implemented without prior written IRB/IEC approval except as necessary to eliminate immediate safety hazards to patients. A protocol amendment intended to eliminate an apparent immediate hazard to patients may be implemented immediately, provided the IRBs are notified within five working days.

10.2 INSTITUTIONAL REVIEW BOARDS AND INDEPENDENT ETHICS COMMITTEE

The protocol and consent form will be reviewed and approved by the IRB/IEC of each participating centre prior to study initiation. Serious adverse events regardless of

causality will be reported to the IRB/IEC in accordance with the standard operating procedures and policies of the IRB/IEC, and the Investigator will keep the IRB/IEC informed as to the progress of the study. The Investigator will obtain assurance of IRB/IEC compliance with regulations.

Any documents that the IRB/IEC may need to fulfil its responsibilities (such as protocol, protocol amendments, Investigator's Brochure, consent forms, information concerning patient recruitment, payment or compensation procedures, or other pertinent information) will be submitted to the IRB/IEC. The IRB/IECs written unconditional approval of the study protocol and the informed consent form will be in the possession of the Investigator before the study is initiated. The IRB/IECs unconditional approval statement will be transmitted by the Investigator to the Sponsor or designee prior to the shipment of study supplies to the site. This approval must refer to the study by exact protocol title and number and should identify the documents reviewed and the date of review.

Protocol and/or informed consent modifications or changes may not be initiated without prior written IRB/IEC approval except when necessary to eliminate immediate hazards to the patients or when the change(s) involves only logistical or administrative aspects of the study. Such modifications will be submitted to the IRB/IEC and written verification that the modification was submitted and subsequently approved should be obtained.

The IRB/IEC must be informed of revisions to other documents originally submitted for review; serious and/or unexpected adverse events occurring during the study in accordance with the standard operating procedures and policies of the IRB; new information that may affect adversely the safety of the patients of the conduct of the study; an annual update and/or request for re-approval; and when the study has been completed.

